9.2 Assessments of outcomes

9.2.1 Assessment of primary outcome

The primary outcome utilises the Desirability of Outcome Ranking (DOOR) and is comprised of the following 4 assessments:

- i) "Alive on day 90" and "return to usual level of function by day 90" will be documented by local investigators or delegated staff. Participants who did not die during hospitalisation will be called on day 90 (± 7 days). If a routine patient visit coincides with this time point, the assessment may be done in person. If the participant can't be reached, the local investigator or designated personnel will make at least 5 attempts at different times of the day to reach the participant. If these fail, reasonable attempt will be made to acquire the information from relatives, caregivers, or the participant's emergency contact or primary care physician.
- ii) During the phone call at day 90 (± 7 days), the participant will be asked to rate their level of function in the 4 weeks prior to their bacteraemia and their current level of function from 6 to 1 according to the modified functional bloodstream infection score¹⁰⁴.
 - 6: Out of hospital, able to complete daily activities without assistance (no limitations)
 - 5: Out of hospital, able to complete daily activities without assistance but with some limitations (e.g. slow, pain)
 - 4: Out of hospital, unable to complete daily activities without assistance
 - 3: Out of hospital; significant disability; requires a high level of care and assistance daily (this includes residential aged care and nursing homes)
 - 2: Hospitalised (or equivalent)
 - 1: On palliative care in terminal phases of life (in hospital or at home)

Baseline is defined as the best score within the 4 weeks before randomisation. If the participant is alive but unable to answer the questions, their caregiver, relatives, or primary care physician will answer the questions to their best knowledge.

- iii) "Complications" will be assessed by evaluation of the participant during hospitalisation either by direct observation or by laboratory assessments. The data are accessed from hospital information systems and entered into the RedCap® database by the local investigator or designated personnel.
 - a. Microbiological failure: Any positive sterile site culture with *S. aureus* between 14 and 90 days after randomisation. A sterile site means any site of the body where microorganisms are usually absent, i.e. below the outer and inner colonised surfaces of the skin and mucous membranes. Positive sterile sites cultures include deep visceral and musculoskeletal abscesses obtained in a sterile manner.
 - b. Clinical failure: Newly identified focus of *S. aureus* between 14 and 90 days after randomisation as determined by the site investigator. This can incorporate clinical, radiological, microbiological, and pathological findings.
 - c. Treatment change: This includes any type of adaptation of the treatment such as new intervention or surgery, or re-start, prolongation or change of antibiotic treatment initiated and documented by the treating physician.
 - d. Serious adverse reactions are assessed and documented by the treating physician.
 - e. Any adverse event (irrespective of grade) leading to study drug discontinuation is documented by the treating physician.

"Complications" a and b will be routinely captured in the eCRF by the local investigator (or a delegated physician), based on hospital information system data on day 28, 42, and 90 and at the day of hospital discharge. An independent and blinded outcome assessment board will review all microbiological and clinical failures to ensure consistency.

On day 90, information on treatment changes ("complication" c) will be assessed from hospital information system data. SAE ("complication" d) will be documented as soon as an investigator becomes aware of a SAE (see chapter 10.1.1 *Definition and assessment of (serious) adverse events and other safety related events*). For all serious adverse events (SAEs), the independent and blinded data safety monitoring board (DSMB) will review any suspected relation to the study drug (defining the SAE as an SAR). In cases where the participant is transferred to another hospital, the local investigator must contact the new hospital to assess the hospital length of stay and potential SAE. Adverse events ("complication" e) will be assessed

as outlined in chapter 9.2.4 *Assessment of safety outcomes*.

- iv) "Hospital length of stay" corresponds to the duration of the acute hospital stay from the day of randomisation into the LIPS trial until day of hospital discharge. These data are assessed using hospital information system data. In case participants are transferred to another acute care hospital ("new hospital"), the local investigator (or delegated personnel) must contact the "new hospital" to receive the information when the participant was discharged from the "new hospital". Outpatient parenteral antibiotic treatment or transfer to rehabilitation centres are not part of the acute hospital stay.

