Rank	Alive at 90 days	Return to usual level of function by day 90	None of the following complications:	Hospital length of stay																								
1	Yes	Yes	Yes (no complications occurred)	Ties will be resolved using the length of hospitalisation																								
2	Yes	Yes	No (complication occurred)																									
3	Yes	No	Yes (no complications occurred)																									
4	Yes	No	No (complication occurred)																									
5	No	Not applicable	Not applicable	Not applicable																								

Table 1: Desirability of Outcome Ranking (DOOR) outcome used for the LIPS trial

Secondary outcomes:

Day of randomisation is defined as day 1.

- All-cause mortality at 90 days
- Time to death up to day 90
- Proportion of participants back to their usual level of function at day 90
- Microbiological failure at 14-90 days leading to treatment change
- Early microbiological failure at 5-13 days leading to treatment change
- Clinical failure at 14-90 days leading to treatment change
- Early clinical failure at 5-13 days leading to treatment change
- Hospital length of stay after randomisation
- Time to being discharged alive (assessed by day 90)
- Number of days without being on the Intensive Care Unit (ICU) up to day 90
- Number of days alive and free of antibiotics up to day 90
- Mental health at day 90 (SF-36 questionnaire)
- Physical health at day 90 (SF-36 questionnaire)

	
 Persistent bacteraemia: S. aureus-positive blood culture on day 5 ≥ 2 systemic inflammatory response syndrome (SIRS) criteria on day 5 Change in C-reactive protein on day 5 Development of new antibiotic drug resistance in Staphylococcus aureus 
Adverse events/safety:
 
 Serious adverse reactions until day 90 Adverse events leading to study drug discontinuation Adverse events of special interest: clinical signs of serotonin toxicity, laboratory signs of myelosuppression, hyperlactataemia, acute kidney injury, Clostridioides difficile-associated diarrhoea within 90 days
Study design:	Multi-centric, 1:1 randomised, parallel group, placebo-controlled clinical trial with blinded participants, physicians, and outcome assessors conducted in the acute-care hospital setting.

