Measurements and procedures:	
Infectious disease specialists, serving as the local principal investigators at all participating centres, are routinely involved in the care of patients with S. aureus bacteraemia. Hence, study teams at all participating sites will consider each patient with S. aureus bacteraemia for potential inclusion in the LIPS trial. The local investigators (or designated staff) will check inclusion and exclusion criteria, initiate the contact, and inform the patient (or a close relative or an independent physician if patient is incapable of judgement) about this trial. After the written informed consent is obtained, the participant will be randomised to the intervention group (i.e. linezolid 600 mg tablets, twice daily for 5 days in addition to standard of care antibiotic treatment) or the control group (i.e. placebo tablets in addition to standard of care antibiotic treatment). The LIPS trial will mainly use data generated as part of clinical routine during hospitalisation. In brief, baseline data (e.g., date of birth, gender, risk factors), microbiological results (e.g., blood culture results, resistance patterns), laboratory results (e.g., blood count, renal function), and data of concomitant treatments (standard antibiotic, source control procedures) will be collected from the hospital electronic medical records. Participants will be treated and monitored according to clinical routine. If a physician suspects an adverse event (e.g. serotonin toxicity, myelosuppression) they should order any assessments and tests necessary for the detection, as in routine clinical practice.
 
The outcomes "alive at day 90" and "return to usual level of function by day 90" will be assessed through a phone call on day 90 (given that the participant did not die during the hospitalisation). In addition, the participants will receive a questionnaire at day 90 to assess their quality of life (QoL, i.e. physical health and mental health).

Study Product / Intervention:	Participants in the intervention arm will receive linezolid 600 mg tablets (twice a day for 5 days) in addition to standard of care antibiotic treatment.
Control Intervention:	Participants in the control arm will receive oral placebo tablets (twice a day for 5 days) in addition to standard of care antibiotic treatment.

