DOOR comprises five ranks (Table 3: Desirability of Outcome Ranking (DOOR) outcome used for the LIPS trial). This outcome is assessed at day 90. The overall distribution of rankings can then be compared between the control and intervention arms, with the final treatment effect estimate being the win ratio, i.e., the probability that a participant randomly assigned to the intervention arm has a superior DOOR compared to a participant randomly assigned to the control arm⁹⁹ (see section 11 STATISTICAL METHODS).

Rank	Alive at 90 days	Return to usual level of function by day 90	None of the following complications:	Hospital length of stay
1	Yes	Yes	Yes (no complications occurred)	Ties will be resolved using the length of hospitalisation
2	Yes	Yes	No (complication occurred)	
3	Yes	No	Yes (no complications occurred)	
4	Yes	No	No (complication occurred)	
5	No	Not applicable	Not applicable	Not applicable

Table 3: Desirability of Outcome Ranking (DOOR) outcome used for the LIPS trial

Detailed definitions of DOOR components:

Alive at 90 days: defined as alive at 90 days after randomisation

Return to usual level of function by day 90: defined as return to baseline value (or better score) according to the modified functional bloodstream infection score¹⁰⁴. Baseline is defined as the best score within the 4 weeks before randomisation. The scores used will be the following:

- 6: Out of hospital, able to complete daily activities without assistance (no limitations)
- 5: Out of hospital, able to complete daily activities without assistance but with some limitations (e.g. slow, pain)
- 4: Out of hospital, unable to complete daily activities without assistance
- 3: Out of hospital; significant disability; requires a high level of care and assistance daily (this includes residential

aged care and nursing homes)

2: Hospitalised (or equivalent)

1: On palliative care in terminal phases of life (in hospital or at home)

Complications:

- Microbiological or clinical failure leading to treatment change: This includes any type of adaptation of the treatment such as new intervention or surgery, or re-start, prolongation or change of antibiotic treatment

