9.3.15 Assessment of clinical failure (day 14, day 28, discharge day, day 90)

“Early clinical failure” and “clinical failure” are defined as the identification of any new focus of *S. aureus* between 5 and 13 days, or 14 and 90 days after randomisation, respectively. This encompasses not only microbiological findings (i.e. detection of *S. aureus*) but also clinical, radiological and histological results. Clinical failure will be assessed by screening of patient history on multiple levels in the available electronic health records and during the telephone call at day 90: any change of the initial antibiotic (and/or surgical) treatment plan will be analysed if it occurred due to proven or assumed new focus of *S. aureus*. Further, all available microbiological results, histological results as well as radiological exams will be screened for signs of newly identified *S. aureus* focus/foci. In case of ambiguous interpretations, the treating physicians can be contacted directly to inquire his/her interpretation of the results. The principal investigator of each site will finally decide if a clinical failure occurred. Furthermore, a blinded panel of experts, selected by the trial investigators, will review each documented clinical failure on a case-by-case basis.

9.3.16 Assessment of length of hospital stay and length of ICU stay (discharge day)

At the time of acute care hospital discharge, the length of hospital stay will be documented according to the hospital records. Similarly, length of stay on the ICU will be extracted from the electronic hospital records.

9.3.17 Assessment of all-cause mortality (day 7, day 14, day 28, day 90 ±7)

The data will be examined in both the hospital records and, when available, external documents to ascertain whether the participant has died during the follow-up period. If the participant cannot be reached for the 90-day telephone follow-up, their emergency contact or primary care physician will be contacted. Documentation of the presumed cause of death is not mandatory.

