9.3.18 Assessment of return to usual level of function (day 90 ±7)

During the phone call at day 90, the participant will be asked to rate their level of function in the 4 weeks prior to their bacteraemia and their current level of function from 6 to 1 according to the modified functional bloodstream infection score (see chapter 5.1 *Primary Outcome* for the corresponding scale). All levels of the scale will be presented orally in a clear and precise manner, ensuring that the participant has adequate time to self-assess. In the event of any misunderstanding regarding the classifications, the scale will be repeated as necessary. If the participant is unable to perform the self-assessment (whether due to medical reasons or limited communication abilities over the phone), efforts will be made to contact a family member or the participant’s primary care physician to obtain the information.

9.3.19 Assessment of physical and mental health (quality of life, SF-36, day 90 ±7)

Quality of life (i.e. mental health and physical health) will be assessed at day 90 through the SF-36 questionnaire. Participants will have the option to complete it either electronically or on paper. At the time of enrolment in the study, participants will be asked which method they prefer. For the electronic version, participants will be requested to provide their email address and/or mobile phone number. This information will be encrypted and accessible only to the local Investigator of the respective centre. On day 90, participants will be notified via email or mobile phone

message about the task and will be directed to the corresponding online version of the study-specific SF-36 questionnaire. For participants who prefer the written version, a letter with a printed version of the SF-36 questionnaire will be sent by postal mail, including an envelope for returning the filled questionnaire. We expect that participants will need approximately 10 minutes to complete the questionnaire. At the time of the 90-day telephone call, participants will be asked whether they have already completed the questionnaire and if they have any questions regarding it. It is not intended for the questionnaire to be filled out verbally over the phone, as this could potentially introduce bias.

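### The close-out call that documents survival at 90 days may be made from day 83, and nothing requires a check on or after day 90, so a few late deaths and out-of-centre events can be missed

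*Protocol*

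**What the plan says.** Section 5.1 defines the top DOOR component at a fixed date: "Alive at 90 days: defined as alive at 90 days after randomisation". The same section counts microbiological and clinical failure up to 90 days after randomisation. The flow chart in section 9.1 has SAEs and SARs collected until day 90.

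The contact that documents survival after discharge is a telephone call. Section 9.2.1 states "Participants who did not die during hospitalisation will be called on day 90 (± 7 days", which allows days 83 to 97. The synopsis gives no window: survival and function "will be assessed through a phone call on day 90 (given that the participant did not die during the hospitalisation". In the flow chart the ±7 days apply to the whole close-out column.

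The same call also collects:
- function, the second DOOR component (9.2.1, 9.3.18);
- whether microbiological samples were taken outside the centre (9.3.14), and part of the screening for new foci (9.3.15);
- post-discharge SAEs and SARs (9.3.12).

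Other sources exist. Under 9.3.17, hospital records and any available external documents are examined "to ascertain whether the participant has died during the follow-up period". Under 9.2.1, failures are captured "based on hospital information system data on day 28, 42, and 90 and at the day of hospital discharge", and treatment changes are taken from the same system on day 90. Length of stay comes from hospital data or the receiving hospital.

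A third party is asked about survival only when the call fails (9.3.17): "If the participant cannot be reached for the 90-day telephone follow-up, their emergency contact or primary care physician will be contacted".

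The SF-36 is issued on day 90 by electronic notice or by post (9.2.2, 9.3.19). Section 9.3.19 adds: "At the time of the 90-day telephone call, participants will be asked whether they have already completed the questionnaire".

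**The concern.** A call made before day 90 cannot establish that someone was alive at day 90, nor rule out events up to that date. A site that reaches a participant on day 83 has met the protocol. Because the participant was reached, the route through the emergency contact or primary care physician is not used. Nothing then obliges anyone to confirm survival once the 90-day date has passed.

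A death after an early call could leave a participant in ranks 1 to 4 instead of rank 5. Survival decides pairwise comparisons first, so this affects the primary outcome directly, and also 90-day mortality and time to death. Infections diagnosed elsewhere and post-discharge SAEs or SARs in the same gap are exposed too.

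This is a matter of data collection. An analysis plan cannot recover vital status that nobody ascertained.

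**Working it through.** **Dates.** Earliest permitted call: 90 − 7 = day 83, leaving 7 days unobserved. The synopsis adds "Day of randomisation is defined as day 1". Read literally, 90 days after randomisation is then study day 91, and the gap is up to 8 days. The calculation below uses 7.

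**Is a later check required?**

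| Source | Timing in the Protocol | Closes the gap for survival? |
|---|---|---|
| Call (9.1, 9.2.1) | Day 90 ±7 | Not if made on days 83–89 |
| Emergency contact or primary care physician (9.3.17) | Only if the participant is not reached | No |
| Hospital and external records (9.3.17) | Heading says day 90 ±7 | Not necessarily |
| Hospital data on failures and treatment change (9.2.1) | Day 90, no window; flow chart and 9.3.14 heading say ±7 | In-centre events only |
| ICU days (9.2.2) | After day 90 | In-centre deaths by chance; not tied to vital status |

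No row requires vital status to be confirmed on or after day 90 when the call was early.

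**Deaths at risk.** The plan states no figure to reproduce. Inputs from section 11.2: 303 per arm; 90-day mortality p = 22.5% (control) and 20.3% (linezolid). The shape of the mortality curve is not given. I assume Weibull curves matched to p at day 90:

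S(t) = exp[−H (t/90)^k], with H = −ln(1 − p), so H = 0.2549 (control) and 0.2269 (linezolid).

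Deaths between days 83 and 90 per arm = 303 × [S(83) − S(90)]. Control, k = 1: S(83) = exp(−0.2549 × 83/90) = 0.7905, and 303 × (0.7905 − 0.7750) = 4.7.

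| Shape k | Control | Linezolid | Total if every call is on day 83 | Total if calls are even over days 83–97 |
|---|---|---|---|---|
| 1.0 (constant hazard) | 4.70 | 4.30 | 9.0 | 2.2 |
| 0.7 | 3.32 | 3.04 | 6.4 | 1.6 |
| 0.5 (deaths mostly early) | 2.39 | 2.18 | 4.6 | 1.1 |

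The last column is about a quarter of the one before it: half the calls precede day 90, and those leave on average half of the 7 days unobserved.

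**Scale.** Expected deaths are 303 × 0.225 + 303 × 0.203 = 68.2 + 61.5, about 130. The even spread puts 1.1/130 to 2.2/130 at risk, about 0.9% to 1.7%. If every call were on day 83, it would be 4.6/130 to 9.0/130, about 3.5% to 6.9%.

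**Effect on the contrast.** The planned difference is 68.2 − 61.5 = 6.7 deaths. With all calls on day 83 it shrinks by 2.39 − 2.18 = 0.2 to 4.70 − 4.30 = 0.4 deaths. With an even spread it shrinks by a quarter of that, about 0.05 to 0.1.

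**SF-36.** Dispatch is on day 90. A call on days 83 to 89 asks about completion of a form that has not been sent. The heading of 9.3.19 gives ±7 although its text fixes dispatch on day 90.

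**The case against.** A symmetric window around a follow-up call is common, the target is day 90, and most late deaths will surface somewhere. Records are searched for deaths, mortality is to be assessed until day 90, death is itself an SAE collected until day 90, and hospital data are consulted after day 90 for ICU days. That a site would record survival on day 83 and close the item is an inference; the Protocol does not say so. These points stand. They make the figures above upper bounds and the wording *can be missed*, not *are missed*. They do not supply the missing rule, and a death outside the centre may leave no trace in its records.

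Stronger readings are tempting, but the documents do not support them:
- *The call decides the rest of the DOOR.* In-centre failures, treatment changes and length of stay come from hospital data. The call supplies function, much of post-discharge vital status, out-of-centre cultures and foci, and post-discharge SAEs or SARs.
- *The loss rivals the planned effect.* The total missed over both arms is not comparable with a between-arm difference of 6.7 deaths; that difference shrinks by at most 0.4.
- *The result is biased towards one arm.* The trial is blinded and both arms share one window.
- *The SF-36 loses its only prompt.* Participants get their own notice or letter on day 90, and calls on days 91 to 97 can ask usefully about completion.

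Moving the whole window later also has a cost. Function is rated as current at the call, whereas the component is return by day 90.

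**Conclusion.** The concern holds in a limited form. A compliant call on days 83 to 89 can document survival at 90 days with up to 7 days unobserved, and no section requires confirmation on or after day 90. The expected effect is a slight under-count: about 1 to 2 of roughly 130 deaths if calls spread evenly over the window, and about 5 to 9 as an upper bound if all were on day 83. These figures rest on the planned mortality rates, the assumed Weibull shapes and the assumed timing of calls, and they take no credit for deaths found in records. Out-of-centre infections and post-discharge SAEs or SARs are exposed in the same way; the Protocol gives no rates from which to size that.

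The case for a change rests on an avoidable misclassification in the first-ranked component of the primary outcome, not on a threat to the trial's conclusion. The SF-36 point is a sequencing fault confined to calls before day 90.

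**What to change.** In sections 9.1, 9.2.1, 9.3.12, 9.3.14, 9.3.15 and 9.3.17, state that vital status and DOOR events are not finalised before the 90-day date. Either:

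1. open the close-out window at that date, with no call before it; or
2. keep ±7 days for function, and require a vital-status and record check on or after day 90, covering out-of-centre events, for anyone called early.

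Under either option, count only events dated up to day 90, and say whether that means study day 90 or 90 days after a randomisation numbered day 1. In 9.3.19, place the call after dispatch of the SF-36 and reconcile the heading with the text.

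The cost is protocol wording and a date check in the eCRF. Option 1 means function is rated a few days later on average. Option 2 avoids that but adds a short re-check for each early call; if the call itself is kept early, the SF-36 question has to be asked at that later contact.

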Number of Participants with Rationale:	
606 participants (303 in control and 303 in the intervention group)
 
We will use the win ratio to assess if participants in the intervention group have a better overall clinical outcome as defined by the DOOR compared to participants in the control group taking the following domains into considerations: i) survival, ii) participant-reported level of functioning at 90 days compared to the level before the blood infection, iii) treatment change due to persistence or spread of the bacterium within day 14-90 or serious adverse events leading to study drug discontinuation, and iv) hospital length of stay in days.
 
The sample size was calculated using a simulation approach (including missing data in the assumptions), for which 1000 synthetic datasets for each combination of plausible values for the relevant parameters were generated and the intended primary analysis was applied. With a two-sided significance level of $\alpha=0.05$ and a desired power of 90% (1:1 allocation), an estimated 550 participants will be required to show a significant effect of the intervention. Because of possible post-randomisation withdrawal due to missing retrospective consent, the sample size was increased by 10% to minimise the risk of being underpowered.
 
See section 11 STATISTICAL METHODS for detailed assumptions about (i) occurrence of events and potential effect for each DOOR domain and (ii) about the frequency of missing data for each DOOR domain.

Study Duration:	
Estimated duration for the main investigational plan (e.g. from start of screening of first participant to last participant processed and finishing the study):
 
38 months

Study Schedule:	
First patient in: September 2025
 
Last patient out: October 2028

Local site- Investigators:	Please refer to the separate document "LIPS list of project leaders" for detailed information on local investigators.
Study Centres:	Approximately 12 institutions in Switzerland will be involved in this multi-centric trial. Please refer to the separate document "LIPS trial sites" for the complete list.
Statistical	Primary analysis:

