 - Microbiological failure: Any positive sterile site culture with *S. aureus* between 14 and 90 days after randomisation. A sterile site means any site of the body where microorganisms are usually absent, i.e. below the outer and inner colonised surfaces of the skin and mucous membranes. Positive sterile sites cultures include deep visceral and musculoskeletal abscesses obtained in a sterile manner.
 - Clinical failure: Newly identified focus of *S. aureus* between 14 and 90 days after randomisation as determined by the site investigator (or delegated physician). This can incorporate clinical, radiological, microbiological and pathological findings.
- Serious adverse reaction (SAR, see definition below)
- Any adverse event (irrespective of grade) leading to study drug discontinuation

Hospital length of stay: This corresponds to the duration of the index acute hospital stay from randomisation until the day of hospital discharge. Transfers to another acute care hospital for continuation of acute treatment will be included in the assessment of hospital length of stay. Days after transfer to rehabilitation centres or switch to outpatient parenteral ambulatory treatment will not be included in the acute hospital stay.

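### Section 9.2.1(iii) separates treatment change from failure in the complications component of the DOOR, which contradicts the definition in section 5.1

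*Protocol*

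**What the plan says.** Section 5.1, under its detailed definitions of the DOOR components, makes treatment change the consequence of a failure: "Microbiological or clinical failure leading to treatment change: This includes any type of adaptation of the treatment". Both failures are confined to days 14-90: "Microbiological failure: Any positive sterile site culture with *S. aureus* between 14 and 90 days after randomisation", and "Clinical failure: Newly identified focus of *S. aureus* between 14 and 90 days after randomisation as determined by the site investigator". Serious adverse reactions and adverse events that stop the study drug are the other two complications.

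The synopsis, in its sample-size rationale, keeps the same link and window: "treatment change due to persistence or spread of the bacterium within day 14-90 or serious adverse events leading to study drug discontinuation" (the second half of that phrase is not at issue here). Section 5.2 and the synopsis list of secondary outcomes also tie each failure to a treatment change. Sections 9.3.14 and 9.3.15 consider changes to the initial treatment plan only where they were due to *S. aureus* at a sterile site or to a new focus.

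Section 9.2.1(iii) sets the component out as five parallel items, a to e. Item a reads "a. Microbiological failure: Any positive sterile site culture with *S. aureus* between 14 and 90 days after randomisation" and has no treatment-change condition; item b, clinical failure, has none either. Item c reads "Treatment change: This includes any type of adaptation of the treatment such as new intervention or surgery". It goes on to include restarting, prolonging or changing antibiotics, and names neither a failure nor a window. The text that follows labels it a complication in its own right: "On day 90, information on treatment changes ('complication' c) will be assessed from hospital information system data". Sections 1.3 and 9.2.1 give the blinded outcome board items a and b to review, but not c.

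**The concern.** The complications component separates rank 1 from rank 2 and rank 3 from rank 4, and it is compared before hospital stay. Two sections of one protocol give different rules for it. Items d and e in 9.2.1 do count on their own under 5.1, and nothing in 9.2.1 tells the reader that c is different.

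The conflict runs in both directions. Item c alone would admit a change made for reasons unrelated to failure, such as a switch of the standard antibiotic for intolerance. Items a and b alone would admit a failure that altered nothing. Standard antibiotic treatment lasts at least 2 to 6 weeks (section 8.7), so unrelated changes are possible both before and after day 14. Section 9.2.2 refers to 9.2.1 for the separate DOOR components, so the wording also reaches secondary outcomes.

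**Working it through.** **1. The two rules side by side.**

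- Section 5.1: (a and c) or (b and c) or d or e, with c caused by a or b, and a and b on days 14-90.
- Section 9.2.1(iii), read literally: a or b or c or d or e, with c at any time up to day 90.

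Take a survivor who is back to usual function and has neither d nor e:

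| Course | Rank under 5.1 | Rank under literal 9.2.1 |
|---|---|---|
| Failure on days 14-90 that leads to a treatment change | 2 | 2 |
| Failure on days 14-90, no treatment change | 1 | 2 |
| Antibiotic change unrelated to any failure | 1 | 2 |
| None of these | 1 | 1 |

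For a survivor not back to usual function, read 3 for 1 and 4 for 2. This step needs no assumption.

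**2. Share of pairs the component decides.** Inputs from section 11.2: deaths 22.5% and 20.3%; worse function 25.0% and 21.3% (25.0% × 0.85 = 21.25%); complications 6.3% and 5.0%. Components are treated as independent and missing data are ignored.

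- Pairs tied on survival (both alive) and function: 0.775 × 0.797 × (0.75 × 0.7875 + 0.25 × 0.2125) = 0.398.
- Decided by complications: 0.398 × (0.063 × 0.95 + 0.05 × 0.937) = 0.398 × 0.1067 = 4.2%.
- Left to hospital stay: 39.8% − 4.2% = about 35.5% (unrounded inputs).

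With an assumed complication rate r in both arms, complications decide 0.398 × 2r(1 − r):

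- r = 30%: 16.7%, leaving about 23% to stay.
- r = 50%: 19.9%, leaving about 20%.
- r = 95%: 3.8%, less than planned.

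The effect rises to r = 50% and then falls.

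**3. The planned sample size.** 550 × 1.10 = 605, taken to an even 606, as stated. The 550 itself can be neither confirmed nor refuted, because the protocol does not give the log-normal parameters for stay. In a simulation of the unmatched win ratio with 275 per arm and the protocol's event and missing-data rates, power ran from about 0.52 to 1.00. The inputs varied were median stay (12-22 days), log-SD (0.45-1.0) and the reading of the 20% reduction; a complication coefficient of 0.5 on the log scale was assumed throughout.

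**4. Conditional effect on power.** Two settings give about 90% at 550:

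- A: median 17 days, log-SD 0.45, reduction applied as ln 0.8.
- B: median 12 days, log-SD 1.0, log-mean multiplied by 0.8.

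A share s of participants in each arm was then given an unrelated treatment change, scored as a complication (1000 replicates per cell). The control complication rate becomes 1 − 0.937 × (1 − s).

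| s (assumed) | Control rate | Power A | Power B |
|---|---|---|---|
| 0 | 6.3% | 0.90 | 0.89 |
| 10% | 15.7% | 0.78 | 0.81 |
| 25% | 29.7% | 0.66 | 0.71 |
| 50% | 53.1% | 0.60 | 0.59 |
| 75% | 76.6% | 0.68 | 0.74 |
| 95% | 95.3% | 0.88 | 0.86 |

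Unrelated changes settle pairs at random that hospital stay would otherwise settle. Failures without a treatment change were not simulated, since the protocol gives no rate for them.

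**The case against.** The strongest reply is that the protocol already has a clear governing definition. Section 5.1 is headed as the detailed definition, its link is repeated elsewhere, and 9.2.1 concerns assessment. The a-to-e list can be read as the compound definition broken into elements to collect, since c repeats the second half of the 5.1 wording. The letter labels are loose in any case: the same text attaches d to serious adverse events, although item d is serious adverse reactions. This stands in part. The intended rule can be recovered, and it does not appear that anyone designed a stand-alone treatment-change endpoint. It does not remove the contradiction, because 9.2.1 calls c a complication and drops the condition from a and b.

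A reader might infer more than the documents support:

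- *That routine antibiotic changes will be scored.* No rule joining the five items by *or* is written and no eCRF is shown. The harm arises only if sites or programmers follow 9.2.1 literally.
- *That a planned operation or planned oral step-down counts.* Item c speaks of adapting treatment, and a step already in the plan is not clearly an adaptation.
- *That the trial is underpowered by a known amount.* The rate of unrelated changes and the stay parameters are not in the protocol, and the loss does not grow steadily with that rate.
- *That false positives increase.* If the arms do not differ, changes equally common in both add noise without favouring either.

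**Conclusion.** Sections 5.1 and 9.2.1(iii) contradict each other on a component of the primary outcome and can give the same survivor ranks one step apart. This rests on the text alone. Section 9.2.1 is the outlier and should be corrected to match 5.1, because a primary outcome needs one definition and the 6.3%/5.0% assumption belongs to the failure-linked one.

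The effect on power is illustrative only. It depends on literal use of 9.2.1, on equal rates of unrelated change in both arms, and on stay parameters chosen to give about 90% at 550. Under those assumptions power is roughly 59-81% for shares of 10-75%, lowest near 50%, and 86-88% at 95%. Under the 5.1 wording this issue gives no reason to change the planned sample size.

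**What to change.** Reword 9.2.1(iii) to match 5.1: (a) microbiological failure or (b) clinical failure on days 14-90, in either case leading to a treatment change. Record treatment change as a condition on a or b, and remove its label as complication c. Keep serious adverse reactions and adverse events that stop the study drug as separate items. If the eCRF follows the current list, tie its treatment-change question to a or b in the same way.

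The cost is a wording amendment and, if needed, one branching rule; no additional outcome data are required.

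Asking the blinded board to confirm that the failure caused the change is optional. It would widen the remit stated in section 1.3, and presumably the board's charter, and is not needed to resolve the contradiction.
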